Atypical antipsychotic agents, compared with haloperidol, have a wider variety of reported affinities for CNS receptors, including dopamine, serotonin, adrenergic, and muscarinic receptors.  $^{107,125}$  Ziprasidone an antagonist at  $D_2$ ,  $H_1$ ,  $\alpha_1$ ,  $5\text{-HT}_{2A}$ ,  $5\text{-HT}_{2C}$ , and  $5\text{-HT}_{1D}$  receptors and an agonist at  $5\text{-HT}_{1A}$  receptors.  $^{125,126}$  Like other successful antipsychotic medications, it has high affinity for the  $D_2$  receptor, though this is not the majority of its receptor activity (as seen with haloperidol). It is distinguished from other atypicals by blocking reuptake of norepinephrine and  $5\text{-HT}.^{126}$  As stated above, atypical antipsychotics typically have a lower incidence of EPS versus haloperidol.  $^{112,127}$  A high  $5\text{HT}_{2A}/D_2$  receptor affinity ratio, which is a particularly strong characteristic of ziprasidone, has been correlated with lower propensity for EPS and may be advantageous in treating negative symptoms  $^{126}$  so prevalent in hypoactive delirium. The  $\alpha_1$  receptor affinity of ziprasidone is reduced in comparison to other atypical antipsychotic medications, which may translate into less orthostatic hypotension. It increases central nervous system acetylcholine and through agonism at the  $5\text{HT}_{1A}$  receptor (as seen with the antidepressant and anxiolytic buspirone) can increase dopamine in the cortex, both of which theoretically would be helpful for delirium.

The strikingly divergent receptor affinities of these two classes of antipsychotics adds to the clinical conundrum surrounding the fact that they are both used anecdotally in widely varying rates across the country for treatment of delirium. Thus, in addition to being the first ever adequately powered trial to compare antipsychotics vs. placebo for ICU delirium, MIND-USA will also be a major step toward making evidence-based decisions about which class of antipsychotics is most effective for critically ill delirious patients. Lastly, the trial may begin to shed light on the complex and poorly understood neurophysiologic derangements underlying delirium in critically ill patients. 

MIND-USA Protocol Version: 1.15 Confidential Protocol Date: June 22, 2016 8 of 51

- **2.5 QT Prolongation and Haloperidol and Ziprasidone**. Antipsychotic medications as a class pose a risk of cardiac conduction disturbance and sudden death.  The risk of QT prolongation and torsades de pointes appears to be cross-class.  In fact, haloperidol had the lowest rate ratio for cardiac death among typical and atypical agents in a recent NEJM report. It has been noted that haloperidol's average OTc prolongation at 15 mg/d is 7.1 milliseconds. This modest increase in QTc has rarely been associated with significant arrhythmia risk as long as baseline and "on-treatment" QTc are < 500 ms, which is easy to detect on continuous ECG monitoring as will be used in all ICU patients for MIND-USA. 132,136 The risk is dose-related 130 and greater for haloperidol when > 35mg per day, nearly double the maximum dose to be used in this trial. 131 The incidence of QT prolongation varies with the specific type of atypical antipsychotic. It is considered rare with ziprasidone at 0.06% QTc  $\geq 500$  msec (data from 2004 Up-To-Date report on ziprasidone), and one study found that ziprasidone and haloperidol have equivalent effects on the OTc interval. 138 The clinical significance of this associated OT prolongation is not known, yet the occurrence of arrhythmias (including torsades de pointes) has been reported as rare. In a study using a total of 50mg of IM ziprasidone and 17.5mg of IM haloperidol over 4 hours, the average increase in QTc from baseline in the ziprasidone group was 12.8 msec at Cmax and in the haloperidol group it was 14.7 msec at Cmax. In this study no patient had a QTc interval exceeding 500 msec (data from package insert for ziprasidone).
- 2.6 Route of Administration, Pharmacokinetics, and Drug Interactions of Haloperidol and Ziprasidone. We have an FDA IND for the MIND-USA investigation (IND #104322) that includes three treatment groups (haloperidol, ziprasidone, and placebo). Both study drugs, haloperidol and ziprasidone, may be delivered reliably and with rapid onset via the PO and IM routes, though the IV route is preferable in an ICU setting, where patients frequently do not have enteral access and coagulopathy precludes IM injections. Whereas haloperidol has routinely been administered IV for decades (despite the absence of FDA approval for this route), the IV use of atypical antipsychotics is less common but is reported in case reports  and in one phase I study of healthy volunteers (N=12 received IV ziprasidone with no ill effects). 142 For example, a 47-yr-old mechanically ventilated ICU patient experiencing profound delirium despite multiple doses of haloperidol and sedatives received a 20mg IV bolus of ziprasidone with "dramatic" improvement in restlessness and delirium and no extrapyramidal or cardiac side effects.  In the only report of extrapyramidal side effects due to IV ziprasidone, symptoms completely resolved after treatment with single doses of diphenhydramine and benztropine. 143 Both haloperidol and ziprasidone are greater than 90% protein bound. The mean half-life of haloperidol is 21 hours with N-dealkylation being the predominant pathway of metabolism; all of the metabolites are inactive with the possible exception of an active hydroxyl metabolite. The mean half-life of ziprasidone is 7 to 10 hours, with CYP 3A4 being the predominant isoenzyme involved in metabolism. The IM formulation of ziprasidone contains a solubilizing agent called β-cyclodextrin (in this case, specifically SBE-β-CD) that has been safely used in other IV medications (e.g., itraconazole and voriconazole) at much higher concentrations. 144,145 In fact, in this investigation our dosing range will have around 3% of what is given routinely with voriconazole, and even in study patients with renal impairment, they will only receive around 15-18% of what is given to humans currently with FDA-approved use of IV voriconazole. Haloperidol is extensively metabolized by the liver's CYP2D6, CYP3A4, and CYP1A1 enzymes, 74,146-150 leaving 1% of administered dose excreted unchanged in urine. Haloperidol has metabolic interactions with ~20 drugs. 148,150 but those of considerable hazard are infrequently

MIND-USA Protocol Version: 1.15 Confidential Protocol Date: June 22, 2016 9 of 51

used in ICU patients. Some important candidates to consider include carbamazepine and phenytoin, which can cause increased haloperidol metabolism and lower its levels. Others with the opposite effect, thereby possibly causing increased concentrations of haloperidol, include buspirone, fluoxetine, and itraconazole. When given concomitantly with lithium, CNS toxicity can result. Rather than exclude patients on these agents and thereby lose the ability to advance our understanding through the context of a controlled trial, methods have been designed to collect haloperidol plasma concentrations and to monitor safety parameters, including continuous cardiac monitoring. Ziprasidone is unlikely to cause significant interactions with drugs metabolized by the cytochrome P450 system. There are no clinically significant interactions with lorazepam or other benzodiazepines, narcotics, H2 blockers, propranolol, or lithium.

- 2.7 Placebo "Treatment" of Delirium as the Comparator for the MIND-USA Trial. Justification for a placebo treatment group as the primary comparator for this trial rests on four distinct and firm issues. First, though many delirious ICU patients receive antipsychotics, the majority of delirious patients actually receive no specific treatment, largely due to the fact that delirium, especially hypoactive delirium,  remains unrecognized over 66% of the time in clinical practice.  Of note, < 5% of ICU delirium is pure hyperactive, with the vast majority being hypoactive or mixed type. 153 While delirium monitoring is now available, data from the 2002 survey indicated that fewer than 5% of practicing ICU healthcare professionals used a specific delirium monitoring instrument. 40 Even though this rate is now up to 33% and rising, most delirium in the ICU is not recognized or treated, which serves as the first major rationale for this placebo-controlled investigation. Second, there are no FDA-approved medications for treatment of delirium. Outside of the pilot studies, there are no placebo-controlled trials of any medications to treat delirium in the highest risk patients, namely older medical and surgical ICU patients. Third, it is possible that typical and atypical antipsychotics could induce harmful effects unrelated to delirium or even via adverse effects on delirium itself. As will be presented below, haloperidol could actually precipitate or worsen delirium in ICU patients, and the placebo group of our pilot MIND study experienced no apparent harm. Fourth, and perhaps most importantly, the definitive study must include a placebo comparison to account for spontaneous improvements in delirium. Such equipoise regarding efficacy and safety of any therapy, especially one as routinely yet erratically prescribed as antipsychotics in the care of fragile, delirious ICU patients, presents a solid rationale for the conduct of a landmark. randomized, placebo-controlled clinical investigation that will be accomplished via this MIND-USA trial.
- 2.8 Conclusions on Background Evidence in Support of MIND-USA Trial. Taken together, this background section highlights two main points: (1) There has been an accelerated path of medical research in the area of delirium, especially among the fastest growing segment of the ICU population—older patients with acute potentially life-threatening illnesses—which happens to have the highest rates of delirium. (2) A dilemma in medicine is clinicians who monitor critically ill patients for brain organ dysfunction are posing the same question that geriatricians, psychiatrists, and neurologists have been for 20 years: "If I prescribe the recommended antipsychotics (haloperidol or an atypical antipsychotic) for my delirious patients, will it help them or hurt them?" In addition, many physicians not monitoring objectively for delirium are waiting for level I evidence from a placebo-controlled multi-center trial to inform them whether or not haloperidol should be prescribed, and if so, in whom and for

MIND-USA Protocol Version: 1.15 Confidential Protocol Date: June 22, 2016 10 of 51

what reasons. The MIND-USA Trial has been designed to address this dilemma. Whether positive or negative, this trial will shape practice due to the driving unmet need for hard data to direct delirium management at a time when practice remains random from hospital to hospital, doctor to doctor, and patient to patient. In 2010, equipoise remains regarding efficacy and safety of routinely prescribed typical and atypical antipsychotics in the care of fragile, delirious ICU patients.

# 3.0 Preliminary Studies

- 3.1 Haloperidol is a Possible Precipitant of Delirium. [name], a MIND-USA co-investigator and the site PI at Yale, conducted a prospective observational cohort study enrolling 309 patients aged 60 and older from 2002 to 2004. This study was designed to examine risk factors for ICU delirium, specifically psychoactive drug use. Detailed medication, physiologic, and delirium data (using the CAM-ICU) were collected daily. Median duration of delirium was 3 days. In a multivariable model, receipt of haloperidol (analyzed as a time-varying covariate) was associated with increased delirium duration [OR=1.35 (1.21-1.50), p<0.001], as were benzodiazepine and opioid use [1.64 (1.27-2.10), p<0.001], dementia [1.19 (1.07-1.33), p=.002], and APACHE II score [1.01 (1.00-1.02), p=0.02]. Risk factors for persistent delirium, defined as a continuous episode of ICU delirium that continued to the ward, were examined. Of 173/309 (56%) patients with ICU delirium, 100 (58%) had persistent delirium. Multivariable regression using time-varying covariates showed haloperidol to be a predictor of persistent delirium [2.88 (1.38-6.02), p=0.005], as was age > 75 (2.52, p=0.01) and high dose opioids (2.9, p=0.02). While not conclusive, these data establish equipoise to consider that haloperidol might cause harm.
- 3.2 Pilot Investigation of IV Haloperidol in Titratable Dose Format. [name], a MIND-USA co-investigator and the site PI at University of Colorado, conducted a small pilot study to explore the safety profile of IV haloperidol in addition to standard sedation in delirious mechanically ventilated patients. 162 Once patients met CAM-ICU delirium criteria, they were randomized to either placebo (n=9) or stepped-dose IV haloperidol (n=8) in addition to usual care (including low dose haloperidol) for ICU sedation. Patients in the active treatment group received haloperidol q6 hours with 2 to 4 mg stepped increase or decrease in dose based on presence or absence of delirium. The haloperidol treatment group received 13.1±10.6 mg/d and through open-label use the control group received  $2.3 \pm 1.9 \text{ mg/d}$  (p<0.001). Median duration of intubation was 3.5 d (control) vs. 3 d (intervention, p=0.24), and median durations for ICU stay were 10 d (control) and 8.3 d (intervention, p=0.50). Median Folstein Mini-Mental State Examination (MMSE) scores at ICU discharge were 19.5 (control) and 30 (intervention, p=0.08). Two patients in the control group died. Adverse events included one self-extubation in each group, one patient in each group developed QTc prolongation to  $\geq 500$  msec, one intervention patient experienced paradoxical increase in delirium, and one in the control group had a possible seizure. These preliminary data suggest that titratable dose IV haloperidol was welltolerated and a suitable approach to adopt for a large-scale, definitive, randomized **controlled trial.** The trend towards better MMSE scores in patients who received an average of 13mg/d of haloperidol is consistent with the cognitive change literature recently subjected to meta-analysis,  which reported that overall cognitive performance improves while on haloperidol, high dose (> 10mg/d) vielded similar effect size compared to doses < 10 mg/d.

[figure not shown]
MIND-USA Protocol Version: 1.15 Confidential Protocol Date: June 22, 2016 11 of 51

although doses  $\geq 25$ mg/d had deleterious effects. The MIND-USA investigators want to give the least amount of haloperidol required to balance efficacy with the need in ICU patients to provide some sedation so that breakthrough and potentially deliriogenic sedatives are minimized.

3.3 The MIND Pilot Feasibility Trial. 44 The MIND trial was designed to test the feasibility of a protocol to address the hypothesis that antipsychotic medications will improve the duration of delirium in a safe manner. In conducting the MIND feasibility study, we included both typical and atypical antipsychotics. The MIND trial was double-blind and randomized placebo vs. haloperidol vs. ziprasidone in 103 medical and surgical ventilated ICU patients at 6 centers. 44 Study drug was administered PO or IM because the FDA would not allow IV administration of atypical antipsychotics at that time since they are not available in this formulation, though they indicated they would allow IV haloperidol. The study was exempted by the FDA for an IND. An atypical antipsychotic was included because this class of drugs might have a favorable safety profile as compared with haloperidol and because of varied affinities of atypical antipsychotics at dopamine, serotonin, adrenergic, and muscarinic receptors. 75,107

Ziprasidone was chosen because it is an antagonist at  $D_2$ ,  $H_1$ ,  $\alpha_1$ , 5- $HT_{2A}$ , 5- $HT_{2C}$ , and 5- $HT_{1D}$  and a 5- $HT_{1A}$  agonist. Like other successful antipsychotic medications, it has high affinity for the  $D_2$  receptor, though this is not the majority of its receptor activity. Haloperidol was given in doses of 2.5 to 5 mg ranging from once per day to every 6 hours (i.e., haloperidol dose ranged from 2.5 to 20 mg per day). This moderate dose range, while higher than used by most geriatricians and psychiatrists yet lower

than the range currently used in most ICUs, was

(a) supported by psychiatric "cognitive change" literature, 163 and (b) important in the ICU because haloperidol provides patient sedation. Because sedation is usually perceived as more urgent than resolution of delirium, it will never be plausible to suggest an avoidance of sedatives altogether, though haloperidol could provide a sedative sparing affect. The average amount of haloperidol administered in the MIND pilot was 17 mg/day over a median of 7 days on study drug, and this resulted in a median haloperidol plasma concentration of 4.5 ng/mL [IOR, 2.8-6.07. Notably, the median [IQR] haloperidol plasma concentration in both the placebo and ziprasidone group was 0 ng/mL [0-0]. The protocol for MIND was similar to that of the MIND-USA trial. Treatment groups were balanced at enrollment by age, severity of illness, and admission diagnosis (#1 diagnosis being severe sepsis). The amount of sedatives given (benzodiazepines, propofol, and fentanyl) were balanced between groups over the course of the study. Figure 2 shows that there were no differences in resolution of delirium and coma; other outcomes, such as length of stay, cognition at discharge, and survival, were similar between the three groups. It is important to emphasize that this *pilot feasibility study* was neither intended nor powered to detect differences in these outcomes. We used a modified Simpson-Angus Scale to monitor objectively for EPS and checked an ECG at baseline and at 24 hours after start of study drug to detect QTc prolongation as well as cardiac arrhythmias. No differences in these anticipated study drug-related adverse events were noted between groups.

MIND-USA Protocol Version: 1.15 Confidential Protocol Date: June 22, 2016 12 of 51

# 4.0 Study Objectives and Endpoints

**4.1 Study Objectives**. The primary objective of the MIND-USA study is to determine the efficacy and safety of haloperidol and ziprasidone vs. placebo in critically ill medical and surgical patients with delirium.

#### 4.2 Efficacy Endpoints

**4.2.1 Primary Endpoint**. The primary endpoint of the trial will be **delirium/coma-free days** (**DCFDs**), defined as the number of days alive without delirium or coma during the 14-day Treatment Period (from randomization until day 14 post-randomization). This continuous variable represents duration of time a patient is alive and free of acute brain dysfunction and has been used in other high impact studies.  The MIND-USA study will have tremendous implications for practice based on the outcome of the delirium duration (i.e., DCFD) results even if the secondary outcome of mortality is neutral between the two study groups. Thus, duration of time free of delirium and coma will be the key consideration of whether or not the study is considered positive or negative in the eyes of the medical community and the factor upon which the sample size is determined.

The analysis of this endpoint, as well as all primary analyses, will examine the **Intention-to-Treat (ITT) population**, defined as all patients who are randomized, regardless of receipt of study drug. Secondary analyses of patients who received at least one dose of study drug will also be conducted.

### 4.2.1 Secondary Endpoints

- [1] 30-day, 90-day, and 1-year **survival (Aim 2)**.
- [2] **ICU length of stay**, i.e., time to ICU discharge, represented by readiness for ICU discharge indicated by a physician order for transfer to lower level of care even if a bed availability problems prevent actual discharge from the ICU (**Aim 3**).
- [3] **Ventilator-free days** (VFDs), i.e., days alive and free of mechanical ventilation at 28 days.
- [4] **Co-administration (frequency and quantity) of analgesics and sedatives** will be closely tracked to determine whether benefits of antipsychotics, if present, are due to sedative-sparing effects. Our MIND pilot study reported a trend towards reduced benzodiazepine exposure in the antipsychotic groups (haloperidol and ziprasidone) vs. placebo (p=0.10). Dexmedetomidine use will also be tracked because it is known to be associated with more DCFDs. 45
- [5] **Neuropsychological function** will be assessed using a telephone battery to determine incidence, duration, and severity of cognitive impairment at 90 days and 1 year post-randomization (**Aim 4**). The battery includes tests of memory, attention, reasoning, and executive function.
- [6] Quality of life, functional status (ADLs, IADLs), and psychological outcomes (PTSD) at 90-days and 1-yearas determined by telephone follow-up. Follow-up testing will consist of ADL/IADL,   CAM,  a neuropsychological battery,  EuroQOL quality of life (EQ-5D),  and PTSD/PCL. 

MIND-USA Protocol Version: 1.15 Confidential Protocol Date: June 22, 2016 13 of 51

**4.3 Safety Endpoints**. Arrhythmias (including torsades de pointes), extrapyramidal symptoms, neuroleptic malignant syndrome, thromboembolism, and readmission (ICU and hospital) will be tracked. 

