# 9.0 Reporting of Adverse Events or Unanticipated Problems involving Risk to Participants or Others

A system has been established to report and track clinical outcomes and adverse events (AEs). Study personnel will monitor the safety of subjects and follow them until the event resolves or is explained.

**9.1** Clinical Outcomes (not considered Adverse Events). In this study of critically ill patients who are at high risk for death or other adverse outcomes due to their underlying critical illness, clinical outcomes, including death and organ dysfunction, will be systematically tracked (collected in the CRF) and will be included as part of the safety and efficacy analyses for this study. For the purposes of reporting, death and organ dysfunction will not be recorded as adverse

MIND-USA Protocol Version: 1.15 Confidential Protocol Date: June 22, 2016 29 of 51

events unless the investigator believes the event may have been caused by study drug and is more severe or prolonged than expected given the underlying critical illness (investigator's discretion). This approach—considering death and organ dysfunction as outcomes rather than adverse events and systemically tracking expected safety outcomes for analysis rather than solely recording individual adverse events—is common in ICU trials because these outcomes/events occur commonly in the ICU and this system mandates that data regarding death, organ dysfunction, and expected safety outcomes be tracked systematically for all patients and analyzed appropriately. All clinical outcomes will be systemically tracked throughout the Treatment Period and the Post-Study Drug Period as described in section 7.3.2. Listed below are events that will be tracked as clinical outcomes and will not therefore be required to be reported as adverse events during this study (unless believed to be study-drug related and more severe or prolonged than expected given the underlying critical illness):

- [1] Death. All deaths occurring within the Interventional Trial Phase will be reported on the CRF in the death summary section. For deaths thought to be caused by study drug, a SUSAR (see section 9.2) will be reported along with the death summary.
- [2] Respiratory failure, including need for mechanical ventilation (invasive or noninvasive) or episodes of hypoxemia
- [3] Circulatory failure, including shock (whether requiring vasopressors or not) and cardiac arrhythmias, and hypertension

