- [4] Hepatic failure or injury leading to increased bilirubin
- [5] Renal failure or injury leading to an increased creatinine or acute hemodialysis
- [6] Coagulation derangements leading to thrombocytopenia
- [7] Stroke and neuropsychological dysfunction that is believed to be newly acquired
- [8] Alterations in vital signs (e.g., temperature, respiratory rate, oxygen saturation)
- [9] Thromboembolisms
- [10] ICU readmissions
- [11] Infections
- [12] Self-removal of devices and invasive tubing and/or monitoring equipment
- [13] The following known adverse reactions to antipsychotics:
  - (a) NMS
  - (b) acute dystonia (i.e., muscle spasms and contractions)
  - (c) pseudoparkinsonism
  - (d) atrial and ventricular dysrhythmias
  - (e) hyperglycemia
  - (f) extrapyramidal symptoms (EPS)
  - (g) tardive dyskinesia
  - (h) akathisia
  - (i) QTc prolongation  $\geq$  550 ms
- 9.2 Adverse Events (AEs), Serious Adverse Events (SAEs), and Serious Unexpected Suspected Adverse Reactions (SUSARs). An Adverse Event (AE) will be any untoward medical occurrence for a patient enrolled in the trial that is not tracked as a clinical outcome (see section 9.1), regardless of whether the event is considered study drug-related or not. If a subject experiences an AE after informed consent is signed but before receiving study drug, the event will be reported as an AE not study drug related. Prior to enrollment, study site personnel will note the occurrence and nature of each subject's medical condition(s). During the study, site

MIND-USA Protocol Version: 1.15 Confidential Protocol Date: June 22, 2016 30 of 51

personnel will note changes in these condition(s) and/or the occurrence and nature of any AEs. All AEs occurring during the Treatment Period and/or the Post-Study Drug Period will be recorded on the CRF. This period is the window of time during which study drug-related adverse reactions are expected based on the duration of the study drug administration plus 4 additional days of Post-Study Drug Period (approximately 4-5 elimination half-lives of haloperidol, the longer acting of the two active study drugs). An AE that later meets criteria for an SUSAR between the start of study drug and hospital discharge will be reported as an SUSAR. If study drug is discontinued as a result of an AE, study personnel will document the circumstances leading to discontinuation of study drug.

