- Time frame: 90 days after first ICU discharge

SO7. Hospital readmission

- Description: Readmission to the hospital after index hospital discharge determined by self-report during follow-up interviews.
- o Time frame: 365 days

SO8. Neuropsychological dysfunction

- Description: Assessed using Telephone Interview for Cognitive Status (TICS),
 Digit Span and Similarities from the WAIS-III, Confusion Assessment Method
 (CAM) Telephone version, Paragraph Recall (both immediate and delayed portions) from the WMS-III, Controlled Oral Word Association Test (COWA), and the Hayling Test. These assessments will be scored in standard fashion and will allow us to characterize cognitive impairment across patients.
- Time frame: 3 and 12 months post-randomization

SO9. Quality of life

- Description: Assessed using the Katz ADL, Employment Questionnaire,
 Functional Activities Questionnaire (FAQ), EQ-5D-3L and a Healthcare Utilization
 Survey.
- Time frame: 3 and 12 months post-randomization

SO10. Post-traumatic stress disorder

- Description: Assessed using the PTSD Checklist (PCL-S, event specific version) with respondents instructed to answer questions in reference to the ICU experience.
- Time frame: 3 and 12 months post-randomization

SO11. Torsades de pointes

- Description: Incidence of tachyarrhythmias determined to be torsades de pointes after review by the site primary investigator, DSMB, and coordinating center.
- Time frame: 14 days plus 4-day post-study drug period (if longer than 14 days)

SO12. Extrapyramidal symptoms

- Description: Occurrence and severity of extrapyramidal symptoms as measured by a modified Simpson-Angus Scale, Akathisia Visual Analogue Scale, and a standardized definition of dystonia
- Time frame: 14 days plus 4-day post-study drug period (if longer than 14 days)

SO13. Neuroleptic malignant syndrome

- Description: Incidence of neuroleptic malignant syndrome identified by the clinical team and confirmed by the site primary investigator and coordinating center
- Time frame: 14 days plus 4-day post-study drug period (if longer than 14 days)

7. Analysis Methods

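### The SAP pre-specifies no by-arm analysis of arrhythmias other than torsades or of thromboembolism, although the protocol makes both safety endpoints and exempts them from routine adverse-event reporting because they will be analysed

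*Protocol*

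**What the plan says.** Protocol 4.3, headed as safety endpoints, reads: "Arrhythmias (including torsades de pointes), extrapyramidal symptoms, neuroleptic malignant syndrome, thromboembolism, and readmission (ICU and hospital) will be tracked". Arrhythmia is named as a class, with torsades as one member.

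Protocol 9.1 then defines clinical outcomes that are not treated as adverse events. Cardiac arrhythmias are in item [3], thromboembolisms are item [9], and "atrial and ventricular dysrhythmias" is item [13](d). Events on the list need not be filed as adverse events, with one exception: "unless believed to be study-drug related and more severe or prolonged than expected given the underlying critical illness". Section 9.2 closes the loop by defining an adverse event as "any untoward medical occurrence for a patient enrolled in the trial that is not tracked as a clinical outcome".

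The exemption comes with a commitment. Clinical outcomes "will be included as part of the safety and efficacy analyses for this study", and the stated justification is that "this system mandates that data regarding death, organ dysfunction, and expected safety outcomes be tracked systematically for all patients and analyzed appropriately".

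The SAP's only rhythm outcome is SO11 in section 6: "Incidence of tachyarrhythmias determined to be torsades de pointes after review by the site primary investigator, DSMB, and coordinating center". Its exploratory list adds a description of torsades incidents and no other arrhythmia. Thromboembolism does not appear in the SAP.

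**The concern.** Section 9.1 strikes a bargain that is reasonable in an ICU trial: frequent background events are not filed case by case, and in return they are collected for everyone and compared between arms. For non-torsades arrhythmia and thromboembolism, the SAP leaves out the second half.

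This matters because the primary objective (Protocol 4.1) covers safety as well as efficacy. Protocol 2.4 includes cardiac dysrhythmia and venous thromboembolism among the adverse events reported for antipsychotics, and 7.3.2 lists arrhythmias beyond torsades among the study-drug risks. The SAP's own background (2.1) opens its safety concerns with fatal rhythm disturbances. A report that followed the SAP to the letter would meet its plan on cardiac rhythm with torsades alone and would say nothing planned about clots. If these comparisons were added after unblinding, the definitions, window and denominator would be chosen with the arm results within reach.

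**Working it through.** There is no figure to reproduce. The check matches each endpoint in Protocol 4.3 to the 9.1 list and to every SAP outcome (primary, SO1 to SO13), the exploratory analyses, the adherence section and the analysis methods.

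| Protocol 4.3 item | On the 9.1 exempt list | Planned by arm in the SAP |
|---|---|---|
| Torsades | within [3] and [13](d) | SO11 and exploratory description |
| Other arrhythmias | [3], [13](d) | none |
| Extrapyramidal symptoms | [13](f) | SO12 |
| Neuroleptic malignant syndrome | [13](a) | SO13 |
| Thromboembolism | [9] | none |
| ICU readmission | [10] | SO6 |
| Hospital readmission | not listed | SO7 |

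Counting readmission as one type, 4.3 has five: three carried over whole, one (arrhythmias) in part, one (thromboembolism) not at all. The SAP gives no reason for the difference.

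Next, could another planned analysis pick these events up?

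1. *Adverse-event reporting.* An exempt event becomes an adverse event only if the investigator believes it drug-related and worse than the underlying illness would explain. The SAP plans no by-arm adverse-event summary, so even those events have no pre-specified comparison.
2. *Reasons for holding or stopping study drug.* SAP section 4 describes these within each arm. Under Protocol 7.3.1[6](b), ventricular tachycardia with clinical consequences or needing therapy is a reason for permanent discontinuation, so it would appear. Under 7.3.1[6](e), so would a life-threatening event judged drug-related, which could be a clot; 6.3 adds events judged drug-related, unexpected and serious. Outside this route lie most atrial arrhythmias, ventricular arrhythmias short of the 7.3.1[6](b) criterion, other clots, and anything occurring after study drug has ended.
3. *Shock severity.* Cardiovascular SOFA and lowest mean arterial pressure describe haemodynamics; they do not count arrhythmias.
4. *Expedited reporting and interim analyses.* Protocol 9.3[3] singles out torsades and neuroleptic malignant syndrome. Under 11.5 the interim analyses compare 90-day survival.

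None of these gives an incidence by arm for either endpoint.

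**The case against.** The strongest reply is that nothing is lost. Section 4.3 promises only tracking, 9.1 still commits the data to the safety analyses and the SAP does not revoke that, serious drug-related events remain reportable, and the DSMB may request further safety data and propose analyses (9.5[3]). Several parts of this stand.

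- A reader might infer that arm differences would go unreported or could not be detected. The documents do not support that: 9.1 requires the data on the case report form, and a later analysis is possible. The supportable statement is that no by-arm analysis is pre-specified.
- A reader might infer that a treated ventricular tachycardia, or any pulmonary embolism, is invisible to the SAP. It is not, if it led to study drug being stopped. QTc prolongation that led to a hold would appear in the same description, and survival is analysed as SO1.
- Hyperglycemia is in 9.1[13](e) and 7.3.2 but not in 4.3, so its absence from the SAP is not a dropped endpoint.
- A reader might argue that torsades will be too infrequent for SO11 to inform. Protocol 2.5 does describe arrhythmia reports as rare, but the documents give no rates for this population, so the point cannot be sized.
- Thromboembolism has weaker support as a study-drug harm. It is absent from the risk lists in 7.3.2 and 8.1, and in 9.1 it sits outside the known antipsychotic reactions of item [13].

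What does not stand is the reading of 4.3 as tracking only. Its heading calls these endpoints, and 9.1 promises analysis. Nor can case-by-case attribution in blinded, critically ill patients replace a comparison of arms; 9.1 itself argues for systematic tracking over relying on individual reports.

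**Conclusion.** The point holds in this form. Two declared safety endpoints, arrhythmias other than torsades and thromboembolism, are exempt from routine adverse-event reporting on the promise of analysis, and the SAP plans no by-arm analysis of either. The discontinuation table covers only events that led to study drug being held or stopped. The size is two of five endpoint types affected, one partly and one wholly. The primary outcome, alpha, sample size and mortality analysis are untouched, so this is something that should be fixed rather than a flaw that undermines the trial. The conclusion assumes that the SAP is the full statement of planned analyses, as its section 4 implies, and that the data 9.1 requires were collected; the case report form is not among the documents.

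**What to change.** Before unblinding, add two safety outcomes to SAP section 6, over the SO11 window and in all randomised patients:

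- (a) atrial and ventricular arrhythmias other than torsades, with ventricular tachycardia shown separately;
- (b) thromboembolism.

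For each, give the number and proportion of patients by arm with 95% confidence intervals, and state the event definition and data source. Name the interval method too: SAP section 7 sets out methods for continuous, time-to-event and long-term outcomes but none for a simple in-hospital incidence. Hyperglycemia can be added on the same terms, but is optional.

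The cost is a few lines of SAP text and two descriptive tables, with no new data collection if 9.1 was followed. The Schedule of Events lists a daily rhythm and QTc review but no thromboembolism item, so the source for (b) should be confirmed first; if it cannot be tabulated, the SAP should say so and why. Removing items from the 9.1 exempt list is not a practical alternative, because the SAP already describes enrolment and randomisation in the past tense and prospective reporting could not be restored.
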